# Aims for Phase I:

- 1. Develop a revised BIP manual for individual treatment delivery as a comparison treatment.
- 2. Develop a fidelity measure to distinguish F4C from BIP for therapist fidelity coding.
- 3. Establish acceptability and feasibility of F4C compared to traditional group BIP (BIP-G) and an individually delivered BIP (developed in aim 1 above; BIP-I). We will test the following specific research hypotheses:
  - i. Fathers randomized to F4C will have higher completion rates than those in either the BIP-I or BIP-G treatments.
  - ii. Fathers will report greater working alliance and satisfaction with F4C than either BIP condition
- 4. Assess initial intervention signal of F4C compared with BIP-I (developed in aim 1 above) and a group format BIP-G (current standard of care) program of comparable length. We will test the following specific research hypotheses:
  - i. Fathers receiving F4C will evidence greater improvement in reflective functioning (RF) and emotion regulation post-intervention compared to fathers receiving BIP-I or BIP-G.
  - ii. Fathers receiving F4C will show greater reductions in intimate partner violence (IPV) and child maltreatment (CM) over the 18 weeks of treatment compared to fathers receiving either BIP condition.
  - iii. Fathers receiving F4C will maintain reductions in IPV and CM in the 3 months following treatment.

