Eighteen percent of children in the United States witness Intimate Partner Violence (IPV) in their homes with significant immediate and long-term consequences to physical and psychological health. Exposure to IPV perpetrated by fathers is common among children referred to child protective services with both national and state level data indicating between 30-40% of child welfare reported children are exposed to IPV, which is most often perpetrated by a father figure. Child protective service systems have long focused on mothers in their interventions for both safety and treatment of IPV. Mothers have been tasked with protecting their children from witnessing IPV or risk losing their children.  Further, all the treatment requirements and opportunities are provided to and expected to be carried out by mothers. Fathers are not held accountable nor are they expected to participate in treatments often due to a belief that interventions do not work for this population. This belief comes from several metaanalyses that report near zero effect sizes of current batterer group intervention programs (BIPs). the only broadly available treatment for IPV perpetrators, in reducing violence. Beyond negligible effects, attrition rates, even for court-mandated programs, are high (30-60%) indicating a significant service need. Importantly, even among intervention completers, recidivism rates for BIPs can be 20-30% indicating high intervention failure.  Often, men who continue to use violence following completion of a group BIP are re-referred to the same program or another similar group program of greater length. Others may serve a short jail sentence with no other treatment provided. Families with IPV are frequently involved with child protective services because it is well known that exposure to IPV is detrimental to children and increases their risk for psychosocial and psychiatric difficulties. (12-14) Despite their ineffectiveness child protective services and the courts in many states continue to use completion of BIPs as sufficient to grant child visitation or as evidence that child protective oversight is no longer needed (15, 16)

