# Preliminary Studies F4C development.

First, F4C was developed and piloted by the PI in an outpatient clinic setting. A sample of 10 fathers were referred by child protection and the courts to participate in an open trial of initial feasibility. Completion rates were 80% and all fathers who completed the program remained non-violent during treatment with very high satisfaction indicating good potential for intervention acceptability. Next, using content, treatment manuals, and training materials developed during the pilot study outlined above, [name] trained 12 clinicians in

community mental health clinics to deliver F4C to child protection involved families through a statewide initiative in CT. Based on session fidelity reviews it is clear clinicians have successfully implemented the intervention using the manual and training curriculum. Based on a sample of 73 fathers referred to F4C, 74% completed the program. Importantly 68% of those referred to F4C had previously participated in a BIP. Additionally, fathers self-reported significant improvements

in the intervention targets of emotion regulation and reflective functioning from pre to post intervention (p<.05). There were significant reductions in IPV post-intervention based on mothers and fathers reports (see Figure 2) and significant reductions in child maltreatment risk based on the Parental Acceptance Rejection Questionnaire (t (67) = 6.44, p < .00) These data support F4C's ability to improve hypothesized intervention targets and IPV and child maltreatment outcomes. The current study is needed to provide an initial randomized test of F4C compared to an individually delivered BIP and group BIP. The randomized three group study will allow us to test F4C compared to BIP-I and Group BIP (BIP-G) and indicate whether the individual treatment format is the driving factor OR the content OR both.

3. **Research Plan:** Summarize the study design and research procedures using non-technical language that can be readily understood by someone outside the discipline. If working with a Non-Government Organization (NGO) or other organization, be sure to highlight which are research-only activities and which activities would occur regardless of the research. If working with survey firms, please specify what research activities the research firm will be responsible for.

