# Analytic Plan.

We will use Research Electronic Data Capture (REDCap™), a widely used secure web-based software package designed for clinical trials to collect study data.

Preliminary Analysis: A series of preliminary analyses will be conducted to: (1) characterize the sample, (2) document the internal reliability of measures, (3) check for logical consistency among related variables, (4) identify outlying values that should be considered for truncation, and (5) assess whether there are significant differences in outcomes based on study therapist. Although urn randomization procedures will be used to balance distribution of specific characteristics across treatment groups, we will explore between-group differences in urn variables and other demographics and possible moderators. Data analyses will be done independently and without

knowledge of group assignment, with the participant's group assignment anonymized to "treatment 1" or "treatment 2".

Phase I Hypotheses:

- i. Fathers randomized to F4C will have higher completion rates than those in the BIP-I or BIP-G treatment. Chi-square analysis will be used to examine between group differences in treatment completion.
- ii. Fathers will report greater working alliance and satisfaction with F4C than BIP-I or BIP-G. Analysis of variance will be used to test between group differences in working alliance and client satisfaction.
- iii. Fathers receiving F4C will evidence greater improvement in RF and emotion regulation, IPV, and child maltreatment(CM) compared with fathers receiving BIP-I or BIP-G postintervention. Mixed effects regression will be used to test for between-group differences in RF, emotion regulation, IPV, and CM representing treatment effects associated with F4C versus BIP over time. Separate IPV and CM sum scores will be created. Any instance of IPV or CM by any report (self, co-parent or current partner report on the Timeline Follow Back, child protection or arrest records) will be counted to create a sum score across reports. The Child Interactive Behavior Codes of Intrusiveness and Child Avoidance will be used as our observational measures of CM risk. Total coded RF score as measured by the PDI and self-reported emotion regulation on the DERS will be used to test impact mechanisms of F4C.

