# 4. How was this estimate derived?

Phase I: Seventy-five fathers, the female co-parent of their youngest child, and their child will participate for a total of up to 225 participants. We intend to include all 75 fathers assigned to study interventions for intent to treat analysis. The planned sample size of 75 participants who will provide data for inclusion in our intention-to-treat analysis should provide sufficient power to detect clinically meaningful differences between and within treatment conditions as specified in our primary aims. A sample of 63 people provides power of 80% to detect a standardized treatment group differences at 18 weeks of d = 0.45. For purposes of power estimates, we assumed d = 0.45 will represent a potentially meaningful clinical difference in both our primary and mechanism outcomes. In a pilot study examining F4C on participant IPV effect size for outcome was d = 0.86. We will enroll 75 participants to accommodate a 16% loss to follow-up.

Using these procedures in prior studies, our rate of successful follow-up has ranged from 70-90%. With 280 participant families randomized and an aim of at least 70% completion, we expect to have 196 cases with complete treatment and follow-up data.

**4. Process of Consent/Assent** (*NOTE: When a study includes minors, parent provide permission [not consent] for the child's participation, and the child provides assent for participation)* 

Describe the setting and conditions under which consent/assent will be obtained, including parental permission or surrogate permission and the steps taken to ensure participants' independent decision-making.

Fathers will complete informed consent either in person or online via Yale's REDcap data system, in line with guidance on obtaining informed consent during the COVID-19 pandemic. Each will agree to have their female co-parent contacted for consent of participation of their shared child.

Mothers will complete informed consent related to their own participation and the participation of children in which they are the primary guardian. This will be completed online via Yale's REDcap system..

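### Phase I claims sufficient power for its primary aims, but gives none for the completion hypothesis; on the protocol's own background rates, 25 fathers per arm is mostly well short of 80%

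*Combined protocol and SAP*

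**What the plan says.** Section V, item 4 (How was this estimate derived?) says that the Phase I sample "should provide sufficient power to detect clinically meaningful differences between and within treatment conditions as specified in our primary aims". The support follows at once: "A sample of 63 people provides power of 80% to detect a standardized treatment group differences at 18 weeks of d = 0.45". On the scope of that effect size it adds: "we assumed d = 0.45 will represent a potentially meaningful clinical difference in both our primary and mechanism outcomes". On dropout: "We will enroll 75 participants to accommodate a 16% loss to follow-up". The Power Analysis paragraph of the Analytic Plan (Section IV, item 3) repeats the figure and refers to a Statistical Design and Power Section that is not in the supplied text.

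The first hypothesis under Phase I aim 3 is: "Fathers randomized to F4C will have higher completion rates than those in either the BIP-I or BIP-G treatments". The Analytic Plan lists it first and gives the test: "Chi-square analysis will be used to examine between group differences in treatment completion". The Research Plan allocates 25 fathers to each of F4C, BIP-I and BIP-G, and all 75 are to enter the intention-to-treat analysis. Alpha, sidedness and the contrasts are not stated.

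The completion figures are in the background sections. For F4C: "Based on a sample of 73 fathers referred to F4C, 74% completed the program"; the earlier open pilot of 10 fathers had 80%. For existing BIPs: "attrition rates, even for court-mandated programs, are high (30-60" percent).

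**The concern.** The power claim is tied to the primary aims, which the protocol does not list. Among the Phase I aims only aim 5 is labelled exploratory, so a reader will take the claim to include aim 3.i. The supporting calculation is for a mean difference. Completion is a single binary outcome per father, with no baseline value and no repeated measurement, so whatever correlation or mixed-model gain may lie behind the d = 0.45 figure cannot carry over to it.

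Completion is one of the main results bearing on the acceptability and feasibility aim. If the true advantage is around 20 points, the chi-square test will usually be non-significant. A protocol that promises sufficient power makes it easy to take that result as evidence of no difference.

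**Working it through.** **The plan's own figure.** The dropout step reproduces: 75 × (1 − 0.16) = 63. The 80% does not, under a simple two-group comparison. With power = Φ(d·√[n₁n₂/(n₁+n₂)] − 1.96) and d = 0.45:

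- 21 v 21: Φ(1.458 − 1.96) = 31% (30% with the t distribution)
- 21 v 42, BIP arms pooled: Φ(1.684 − 1.96) = 39% (38%)
- 63 split into two equal halves: Φ(1.786 − 1.96) = 43% (42%)

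Adjusting for baseline would need a baseline-to-outcome correlation of about 0.77 to 0.85 to bring these to 80%. The supplied text states none.

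**Inputs for completion.** n = 25 per arm; F4C 74% or 80%; BIP 40-70% (100% minus attrition of 30-60%), applied to both BIP arms because no BIP-I figure is given. Assumed: alpha 5%, two-sided, with the alternatives shown.

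**One case by hand, 74% v 55%.** Pooled rate 0.645.

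- SE under the null = √(2 × 0.645 × 0.355 / 25) = 0.1353
- SE under the alternative = √[(0.74 × 0.26 + 0.55 × 0.45) / 25] = 0.1327
- Power ≈ Φ[(0.19 − 1.96 × 0.1353) / 0.1327] = Φ(−0.57) = 28-29%
- 95% interval half-width = 1.96 × 0.1327 = 26 points

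**Exact enumeration of the binomials.** Uncorrected chi-square, F4C higher. Power in %, with the two F4C rates given as 74% / 80%:

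| BIP completion | 25 v 25, two-sided | 25 v 25, one-sided | 25 v 50 pooled BIP, two-sided |
|---|---|---|---|
| 40% | 73.2 / 86.7 | 82.0 / 92.1 | 83.7 / 94.2 |
| 45% | 59.6 / 76.7 | 70.5 / 84.8 | 70.7 / 86.9 |
| 50% | 44.8 / 63.8 | 56.6 / 74.2 | 54.3 / 74.9 |
| 55% | 30.8 / 49.3 | 41.8 / 60.9 | 36.9 / 58.8 |
| 60% | 19.2 / 35.1 | 28.1 / 46.3 | 21.8 / 41.2 |
| 65% | 10.7 / 22.8 | 16.9 / 32.2 | 11.1 / 25.5 |
| 70% | 5.3 / 13.2 | 9.1 / 20.2 | 4.9 / 13.8 |

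Two-sided pairwise, 1 of the 14 scenarios reaches 80%. One-sided or pooled, 3 of 14 do: 74% v 40%, 80% v 40% and 80% v 45%. The three-group chi-square with equal BIP arms gives 6-88% over the same range (27% and 47% at BIP 55%).

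**Detectable gap.** For 80% two-sided pairwise power, BIP completion must be no more than about 37% (F4C 74%) or 43% (F4C 80%), a gap of about 37 points. The normal approximation gives 35% and 42% (38-39 points), and a continuity-corrected test needs about 41 points. By the normal approximation, 80% power would need 99 per arm at 74% v 55% and 54 per arm at 80% v 55%.

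**The plan's effect size moved to this outcome.** On the arcsine scale, 0.45 corresponds to 74% v 52.5%: 2·arcsin√0.74 − 2·arcsin√0.525 = 0.45. The exact power for that pair is 38%.

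**The case against.** The best defence is about scope. The primary aims are not listed, the sentences after the claim speak of standardised differences and of primary and mechanism outcomes, and the only measure named as the primary outcome measure is the FSI-R. On that reading completion was never promised 80% power. The reading is possible and no stated completion figure is wrong, but the sentence does not say so, and completion is the first hypothesis in the Analytic Plan.

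The inputs are also open to challenge, and this stands. The BIP attrition range is literature background on existing programmes, not a planning value. BIP-I is developed within Phase I and has no rate at all. The F4C rates come from 10 pilot fathers and a community roll-out. The powers above are therefore scenarios, not forecasts.

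The choice of test matters too. A one-sided or a pooled test does reach 80% when BIP completion is near 40-45%. Neither is specified, and at BIP 55% each stays at or below 61%. Using both together, by the same enumeration, gives 71% at 80% v 55%.

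A reader might infer that Phase I cannot detect any completion advantage, that its acceptability conclusion rests on this test alone, or that the investigators will treat a non-significant result as equality. The documents support none of these. Power is adequate at the favourable edge, working alliance and satisfaction are companion hypotheses analysed by ANOVA, and no section says how a null chi-square would be read. A requirement that F4C be significantly better than both BIP arms (power about 2-78%) is likewise a reading of the hypothesis, not a stated decision rule.

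Finally, the missing power section may hold repeated-measures assumptions that explain the 80% for continuous outcomes. It could not supply them for completion.

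**Conclusion.** The concern holds in a limited form. The sufficient-power sentence is broader than the calculation beneath it, and for completion the supplied text gives no power. With 74-80% for F4C and 40-70% for BIP taken as assumptions, two-sided 5% pairwise power is about 5-87%, with 31% and 49% at the BIP midpoint of 55%. Reaching 80% takes a gap of roughly 35-40 points, depending on the test. If BIP-I keeps more fathers than group programmes do, power for that contrast falls further.

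For the continuous outcomes the conclusion is narrower: the 80% at d = 0.45 with 63 fathers is not reproduced by a simple comparison (about 30-42%), and the assumptions that might justify it are not stated. It would go too far to say that the figure is shown to be wrong.

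**What to change.** In Section V, item 4, and in the Phase I Power Analysis paragraph of the Analytic Plan:

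- Remove completion from the sufficient-power claim. State that 25 fathers per arm gives 80% power only for a completion gap of roughly 35-40 points, and name the alpha, sidedness and contrast assumed.
- Make the F4C minus BIP-I and F4C minus BIP-G completion differences, each with a 95% confidence interval, the feasibility result. Say that a non-significant chi-square will not be read as equal completion.
- For the continuous outcomes, either state the assumptions behind 80% at d = 0.45 (contrast, sidedness, correlation, number of measurements) or drop the figure. Simply limiting the sentence to continuous outcomes would endorse a number that has not been reproduced.

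The cost is protocol wording and two confidence intervals, with no additional participants and no design change. The stated power becomes less favourable.

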Phase I: Seventy five fathers of children aged 6 months to 11 years will be referred by the Department of Children and Families to the Parent and Family Development Program at Yale, recruited and randomized to either F4C BIP-I or BIP-G (n = 25 per group) following an initial screen and baseline assessment.

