- iv. Exploratory hypothesis: Test whether improved RF and emotion regulation are associated with reduced IPV and CM consistent with the F4C mechanisms of change. We will test path models: treatment group (dummy coded F4C, BIP-I or BIP-G) to each mediator (RF, emotion regulation) to the two outcomes (IPV and CM). See Statistical Analysis section for further details.

Power Analysis: A sample of 75 with planned 63 participants with complete data will provide 80% power to detect group differences with a modest effect size of .45 (see Statistical Design and Power Section).

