2. What participant information will you be collecting? Describe the identifiers that will be included or associated with the data and/or specimens (e.g., names, addresses, telephone/fax numbers, email addresses, dates (date of birth, admission/discharge dates, etc.), medical record numbers, social security numbers, health plan beneficiary numbers, etc.)

We will collect names, birth dates, criminal records, Department of Children and Families records and contact information (phone numbers, addresses and email addresses) from study participants. If a participant drops out of the research study we will make efforts to retain them in the study for intent to treat analysis. This information will be kept with the signed informed consent in a locked cabinet in the PI's office. It will not be linked to study measures which will be locked in another office space under the participants study ID number.

Other potentially identifying information to be collected:

⊠Audiotapes

⊠Videotapes

□Faces (focus groups, photographs or other way that an individual would be physically recognized)

Potential for identification from the bulk of the information, even if direct identifiers are not collected (deductive disclosure).

3. How will the research data be collected and recorded?

Data will be collected via interview and entered directly into an on-line REDCap data system. REDCap is an on-line, secure data capture. Responses to the PDI will be recorded via audio recorders. They will be downloaded onto a secure password protected servers that only study team members will have access. Digital recordings will be conducted by the therapist and stored on a HIPAA secure server. They will be rated by trained therapy fidelity coders. All data will be stored on a password protected and encrypted HIPAA compliant server at the Yale School of Medicine and entered on a secure REDCap database.

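### Phase I's 80% power at d = 0.45 cannot be reproduced from its stated inputs; an outcome with one baseline and one 18-week value reaches it only with a high baseline correlation that the plan does not state

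*Combined protocol and SAP*

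**What the plan says.** Section V, How was this estimate derived?, gives the Phase I claim: "A sample of 63 people provides power of 80% to detect a standardized treatment group differences at 18 weeks of d = 0.45". It sets the scope of that effect size: "we assumed d = 0.45 will represent a potentially meaningful clinical difference in both our primary and mechanism outcomes". It concludes that the 75 fathers give "sufficient power to detect clinically meaningful differences between and within treatment conditions".

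The Power Analysis paragraph of the Analytic Plan repeats the claim: "planned 63 participants with complete data will provide 80% power to detect group differences with a modest effect size of .45". This makes clear that 63 is the total with complete data out of 75. It refers to a Statistical Design and Power Section for details.

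The Research Plan (Section IV.3, Phase I) has fathers "randomized to either F4C BIP-I or BIP-G (n = 25 per group".

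For the analysis, Phase I hypothesis iii says "Mixed effects regression will be used to test for between-group differences in RF, emotion regulation, IPV, and CM". It names as outcomes the IPV and CM sum scores, two play-session codes (intrusiveness and child avoidance), self-reported emotion regulation on the DERS, and "Total coded RF score as measured by the PDI".

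On timing:
- The Timeline Followback logs are weekly during treatment, and Table 1 also marks the DERS as weekly.
- The play session is described at baseline and post-treatment (Parent-Child Interaction Tasks; Post intervention). Table 1 adds a 12-month play assessment.
- The PDI has no stated schedule. Beyond hypothesis iii, Section VI says only "Responses to the PDI will be recorded via audio recorders". Table 1 lists RF questionnaires, not the PDI.

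**The concern.** An effect of 0.45 SD with about 21 completers per arm is far from 80% power in an ordinary comparison at one time point. Repeated measures or baseline adjustment can close the gap, but by how much depends on correlations that the plan does not state. One 80% figure is nevertheless attached to outcomes measured on very different schedules.

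The 80% justifies the 75 fathers and the assurance of adequate power between conditions. Section IV.2 (Preliminary Studies) says that the three arms are there to separate the effect of individual format from that of content. That separation rests on contrasts between two arms, which have the least power. A null result on such a contrast, read against a claimed 80%, could be taken as evidence of no difference when the contrast was never likely to show one.

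**Working it through.** **Inputs from the documents.** d = 0.45 at 18 weeks; 63 completers in total; 75 randomised as 25 per arm in three arms; 16% loss; mixed effects regression.

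**Assumed, because not stated.** Alpha 0.05, shown two-sided and one-sided; equal loss across arms, so 63/3 = 21 per arm. Contrasts: F4C against one BIP arm (pairwise), or F4C against both BIP arms pooled.

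**Step 1: the plan's own figures.** The dropout step reproduces: 75 × 0.84 = 63. The power step does not. Power comes from the noncentral t distribution with noncentrality d × √(n₁n₂/(n₁+n₂)) on n₁+n₂−2 df. For 21 v 21 this is 0.45 × √10.5 = 1.458, and for 21 v 42 it is 0.45 × √14 = 1.684.

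| Comparison | Power, two-sided 0.05 | Power, one-sided 0.05 | Detectable d at 80%, two-sided |
|---|---|---|---|
| 21 v 21 | 0.30 | 0.42 | 0.89 |
| 21 v 42 | 0.38 | 0.51 | 0.76 |
| 25 v 25 (all 75 kept) | 0.34 | 0.47 | 0.81 |
| 25 v 50 (all 75 kept) | 0.44 | 0.57 | 0.70 |

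Other readings also miss. A three-arm ANOVA with F4C 0.45 SD from both BIP arms gives 0.29. Reading 0.45 as Cohen's f gives 0.89, and 80% would then need only 51 people. The one simple variant that lands near 80% is 63 per arm, one-sided 0.05 (0.807), which contradicts 63 as a total.

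**Step 2: outcomes with one baseline and one 18-week value.** Adjusting for baseline with correlation r replaces d by d/√(1−r²) and costs one df. The r that brings power at d = 0.45 to 80% is:

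| Comparison | Two-sided 0.05 | One-sided 0.05 |
|---|---|---|
| 21 v 21 | 0.86 | 0.82 |
| 21 v 42 | 0.81 | 0.74 |
| 25 v 25 | 0.83 | 0.78 |
| 25 v 50 | 0.76 | 0.68 |

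With 63 completers at two-sided 0.05 and illustrative values of r:
- r = 0.5: power 0.38 pairwise and 0.48 pooled; detectable d 0.77 and 0.66.
- r = 0.7: power 0.51 and 0.64; detectable d 0.63 and 0.54.
- r = 0.8: power 0.66 and 0.79.

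**Step 3: weekly outcomes, 63 completers, two-sided 0.05.**
- *Baseline-adjusted mean of 18 weekly values, constant correlation ρ.* The variance factor is (1+17ρ)/18 − ρ². At ρ = 0.5 it is 0.528 − 0.25 = 0.278, so d becomes 0.45/√0.278 = 0.85 and pairwise power is 0.77. Over ρ from 0.1 to 0.8, pairwise power runs from 0.77 to 0.97, and pooled power is at least 0.88.
- *The same mean without a baseline value.* 80% needs ρ of at most about 0.21 pairwise or 0.31 pooled.
- *Group-by-time slope over weeks 0 to 18, with a difference of 0.45 at week 18 (normal approximation).* Constant correlation needs an ICC of at least 0.52 pairwise or 0.36 pooled. If the correlation instead decays to 0.5 by week 18, power is only 0.31 and 0.39; if it decays to 0.8, power is 0.64 and 0.76.

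Weekly outcomes therefore range from about 0.3 to above 0.9, depending on inputs that the plan does not give.

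**The case against.** The strongest reply is that the planned analysis is a mixed model, not a t test at 18 weeks. Several Phase I outcomes are collected weekly, and 80% at d = 0.45 with 63 fathers is an ordinary repeated-measures result under plausible correlations. That stands for the Timeline Followback logs and the DERS. A reader might infer from Step 1 that Phase I has only 30% to 40% power throughout, or that 80% is impossible. The documents do not support that: Step 1 is a benchmark, not the power of the planned model.

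Other parts of the reply also stand:
- No alpha is stated and the Phase I hypotheses are directional, so a one-sided test cannot be excluded. It lowers the required baseline correlation but leaves the simple comparison at 0.57 or below.
- The cited Statistical Design and Power Section may hold the missing inputs. What is shown is that the figure is unsupported where it is stated.
- A reader might take PDI-coded RF as certainly measured only before and after treatment. That is an inference. The Post intervention section repeats the baseline RF assessments without naming the PDI, and much of the assessment text describes the two-arm Phase II schedule.
- Phase I looks for feasibility and an initial signal, and the pilot effect was d = 0.86.

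The pilot effect does not rescue the claim, because the plan itself sets 0.45 as the meaningful difference; even at 0.86, 21 v 21 has power of about 0.78. The 12-month play assessment in Table 1 does not add to a comparison at 18 weeks.

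**Conclusion.** The point holds in a limited form. The 80% at d = 0.45 does not follow from the inputs given with it, and it should not cover all primary and mechanism outcomes without distinction. For weekly outcomes it is attainable but undemonstrated.

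For an outcome with one baseline and one 18-week value, 63 completers reach 80% only if the baseline correlation is about 0.86 pairwise or 0.81 pooled at two-sided 0.05, or 0.82 or 0.74 one-sided. The lowest value found, 0.68, needs all 75 fathers, pooled BIP arms and a one-sided test. This applies to the play codes and, if measured only at those two times, to PDI-coded RF.

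The result rests on equal loss across arms and on the assumed alpha. It does not show that Phase I needs more fathers or that the planned analysis is wrong.

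**What to change.** In the Analytic Plan's Power Analysis paragraph and in Section V, How was this estimate derived?:
1. State the alpha, sidedness, contrast, time points and correlation behind the 80%, bringing them in from the cited power section if they are there.
2. Limit the 80% to the outcomes and contrast that a repeated-measures calculation supports. If no such calculation exists, remove the claim.
3. For baseline/post outcomes, give the detectable effect instead. With 21 per arm at two-sided 0.05 (alpha for the sponsor to confirm), d is about 0.89 pairwise or 0.76 pooled, unadjusted. If r = 0.7 is assumed, it is about 0.63 or 0.54, and power at d = 0.45 is about 51% or 64%.
4. State when PDI-coded RF is measured in Phase I.

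The cost is about one paragraph of text, with no extra enrolment and no change of analysis. The downside is a less favourable stated figure for the baseline/post outcomes.
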